3.2 Rationale of study design

This randomized, multi-center, patient and investigator blinded, placebo-controlled study is designed to assess the safety and tolerability of LMB763 relative to placebo in patients with NASH.

Randomization will be initiated at a **2:1** ratio of active to placebo in order to reduce the sample size. The statistical power of the study will be bolstered by using historical control data from trials like the FLINT study to supplement the placebo arm. Multiple sites are necessitated due to the underlying prevalence of NASH defined in publicly available recruitment data. No known differences exist in regional criteria for the histopathological diagnosis of NASH. Since NASH is more common in those self-identified as Asian at lower body mass index (BMI), specific criteria inclusion criteria have been included for this population.

In order to maintain the scientific integrity of the study, the investigator and patient will remain blinded to their treatment allocation and baseline intra-hepatic lipid content. To allow close monitoring of biochemical safety parameters which overlap with efficacy outcomes (eg. ALT) and understanding of performance of exploratory biomarkers, the Novartis Clinical Trial Team (CTT) will be unblinded throughout the study.

To ensure that no bias is introduced by imbalance in severity of disease across different arms of the study, patients will be stratified to active or placebo arms on the basis of BMI.

The duration of 12 weeks of therapy is supported by GLP-toxicology studies of 13 weeks in duration and it is also a suitable timeframe to test the chosen primary endpoints in the study. In the FLINT trial of a less potent FXR agonist, ALT and GGT levels in the blood dropped as early as after 4 weeks of treatment and most of this effect was noted by 12 weeks of therapy ([Neuschwander-Tetri et al 2015](#)).

To keep dietary intake as consistent as possible, patients participating in this study will be instructed to carefully adhere to American Heart Association (AHA) diet or equivalent if there is a country specific recommended diet.

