12. Inability to reliably quantify alcohol consumption based upon local study physician judgment.
13. History of drug or alcohol abuse within the 12 months prior to dosing, or evidence of such abuse as indicated by the laboratory assays conducted during screening and baseline. Marijuana use is not allowed if it is determined to be medically inappropriate by the investigator.
14. Prior or planned (during the study period) bariatric surgery (eg, gastroplasty, roux-en-Y gastric bypass).

15. Type I diabetes and uncontrolled diabetes defined as $HbA_{1c} \geq 9.5\%$ within 60 days prior to enrollment.
16. Calculated eGFR less than 60 mL/min (using the MDRD formula)
17. Presence of cirrhosis on liver biopsy or clinical diagnosis.
18. Clinical evidence of hepatic decompensation or severe liver impairment as defined by the presence of any of the following abnormalities:
 - Serum albumin < 32 g/L
 - INR > 1.3
 - Direct bilirubin > 13 mg/L
 - ALT or AST > 5 × ULN
 - Alkaline Phosphatase > 3 × ULN
 - History of grade 2 or greater esophageal varices, ascites or hepatic encephalopathy
 - Splenomegaly
19. Platelet count < $120 \times 10^9/L$.
20. History or presence of other concomitant liver diseases including, but not limited to:
 - Hepatitis B or C virus (HCV, HBV) infection
 - Primary biliary cholangitis (PBC)
 - Primary sclerosing cholangitis (PSC)
 - Alcoholic liver disease
 - Definite autoimmune liver disease or overlap hepatitis
 - Suspected or confirmed Gilbert's syndrome
 - Known bile duct obstruction
 - Suspected or proven liver cancer
21. History of liver transplantation or current placement on a liver transplant list.
22. History of inflammatory bowel disease.
23. Known positivity for Human Immunodeficiency Virus (HIV) infection.
24. History of non-adherence to medical regimens, or patients who are considered by the investigator to be unable to reliably comply with the requirements of the study.
25. Chronic use (i.e. > 3 months immediately prior to baseline visit) of high dose Nonsteroidal Anti-inflammatory Drugs (NSAIDs) as evaluated by investigator.
26. History or current diagnosis of ECG abnormalities indicating significant risk of safety for patients participating in the study such as:
 - Concomitant clinically significant cardiac arrhythmias, e.g., sustained ventricular tachycardia, and clinically significant second or third degree AV block without a pacemaker
 - History of familial long QT syndrome or known family history of Torsades de Pointes

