6.6 Permitted dose adjustments and interruptions of study treatment

Safety and tolerability

In the event of a significant safety/tolerability concern which does not meet study stopping criteria ([Section 7.5](#)), and is not related to ALT and/or AST elevations, temporary interruption and dose adjustments are permitted as follows in order to allow the patient to continue on study treatment:

- Cohort 1: Reduction in dose frequency to every alternate day
- Cohort 2: Reduction in dose

Investigators must use their medical judgment in regards to what they deem as the best interest of the patient.

Significant isolated ALT and/or AST increase

In the event of a significant ALT and/or AST elevation, temporary interruption and dose reduction is permitted in order to allow the patient to continue on study treatment. The guidance for the modification of study treatment is outlined below and in [Table 6-3](#); this will allow an evaluation of whether such dose reductions are useful in patient management. The ability to reduce the dose is clinically relevant as data generated after dose reduction will provide further information regarding the tolerability and safety of LMB763.

If the patient has symptoms or other LFT abnormalities, in particular elevations of bilirubin and/or PT/INR and/or ALP), refer to [Section 9.3](#) and [Table 9-2](#) for appropriate actions.

Triggers related to ALT and/or AST elevation are described in [Table 9-1](#). A significant ALT and/or AST increase is defined as (i) in the presence of symptoms or other liver function abnormalities $> 3 \times \text{ULN}$, **AND in the case of elevated baseline $> 2 \times \text{Baseline value}$** ; (ii) in the absence of symptoms or other liver function abnormalities ALT and/or AST elevation $> 5 \times \text{ULN}$ **AND in the case of elevated baseline $> 2 \times \text{Baseline value}$** . All cases with ALT and/or AST elevation $> 3 \times \text{ULN}$ will be captured as a liver event per [Table 9-1](#) and instructions for further assessment detailed in [Table 9-2](#). Patients who experience significant isolated ALT and/or AST elevations will be instructed to return to the clinic within 48-72 hours for an additional laboratory evaluation to confirm these results, as defined in [Table 6-3](#). The laboratory tests to be repeated are ALT, AST, GGT, alkaline phosphatase, total bilirubin, and albumin (LFT) and PT/INR.

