The guidance for the modification of study treatment is outlined below in [Table 6-3](#).

If the additional laboratory evaluation confirms a significant increase of ALT and/or AST values, the dose frequency will be reduced to every alternate day (cohort 1), or the dose will be reduced (cohort 2); the investigator and site personnel will remain blinded to the identity of treatment. The investigator must document the patient's dose frequency reduction in source documents.

If the additional laboratory evaluation does not confirm the significant increase of ALT or AST values, the patient will continue with the assigned/original treatment.

If the additional laboratory evaluation shows a higher elevation of ALT and/or AST (e.g. > 8 x ULN) as compared to the original elevation (e.g. > 5 x ULN but < 8 x ULN), the guidance for this higher elevation (e.g. > 8 x ULN) should be followed.

Actions should be based on whichever of AST and ALT has a higher multiple of ULN or baseline value. In order to allow for variation in laboratory results, persisting elevation is defined as the value remaining at $\geq 90\%$ of the original elevated value. When there is a marked difference in multiple of ULN between ALT and AST, medical judgment should be applied to distinguish between persisting and decreasing. If at any time the repeat testing shows levels in a higher category, the guidance for the higher category should be followed.

Only one cycle of dose frequency/dose reduction is allowed. If, despite being on a reduced dose, a patient has persistent or new significant ALT and/or AST elevations, the patient must be discontinued from study treatment (refer to [Section 7.2](#)). After discontinuation for a liver-related event, LFT and clinical monitoring should continue until the event is resolved (refer to [Section 9.3](#)). Increasing the dose to the original level is not permitted.

Table 6-3 Dosing response to Isolated ALT/AST Elevations

ALT and/or AST increase	First Action	Result	2nd Action	Result	3rd Action

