> 2 x baseline AND ≤5 x ULN	Repeat tests ¹ within 48-72 hours	Elevation ² of ALT and/or AST confirmed	Initiate close observation of patient. Repeat tests ¹ within 48 – 72 hours	Persistent elevation ² of ALT and/or AST for 1 week	Cohort 1: Reduce Dose frequency to alternate day dosing Cohort 2: Reduce LMB763 dose Continue close observation of patient with minimum twice weekly testing ¹ (once weekly if stable) until ALT and AST <3x ULN (or 2x baseline if elevated before drug exposure). If ALT and AST levels remain ≥3x ULN three weeks after dose reduction, discontinue study treatment
		Decreasing ALT and AST ³		Continue assigned study treatment as per protocol	
		Decreasing ALT and AST ³	Continue assigned study treatment as per protocol	--	--
> 2 x baseline AND >5 x ULN but ≤ 8 x ULN	Repeat tests ¹ in 48 hours	Elevation ² of ALT and/or AST confirmed	Cohort 1: Reduce Dose frequency to alternate day dosing Cohort 2: Reduce LMB763 dose Initiate close observation of patient. Repeat tests ¹ within 48 – 72 hours	Persistent elevation ² of ALT and/or AST	Discontinue study treatment
		Decreasing ALT and AST ³		Continue with reduced dose frequency or reduced dose Continue close observation of patient with minimum twice weekly testing ¹ (once weekly if stable) until ALT and AST < 3 x ULN and < 2 x baseline. If ALT and AST levels remain ≥3 x ULN three weeks after dose reduction, discontinue study treatment	
		Decreasing ALT and AST ³	Continue assigned study treatment as per protocol	--	--
>2 x baseline AND >8 x ULN	Discontinue study treatment	--	--	--	--

¹Tests: A physical examination should be performed and recorded in source documents. PT/INR, ALT, AST, GGT, alkaline phosphatase, total bilirubin, and albumin; these repeats must be performed using the central laboratory if possible and captured via the unscheduled lab CRF. If this is not possible, then the repeats can be performed at a local laboratory to monitor the safety of the patient. If tests are performed at local laboratory, results will be captured in source documents only.

²Persistent: either ALT and/or AST remain > 90% of the original elevated level

³Decreasing: both ALT and AST levels decrease to ≤ 90 % of the original elevated level. Medical judgement should be applied if there is a marked difference between ALT and AST multiples

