7.5 Study Stopping rules

The severity of adverse events will be graded by the study site Investigator (or designee) based on clinical judgment and captured in the CRF AE page. This information will be used to quantify events that may lead to patient's discontinuation or stopping dose arms or the study.

Study Stopping Rules

The study will be placed on hold to further enrollment, no new patients may be dosed, however dosing of those without safety concerns may continue. The study may be stopped based on a full review of all available clinical safety data and discussion with the Investigators if any of the following occur:

- One patient on study drug experiences any adverse event that is CTCAE Grade 4 or higher that is classified as related to study drug.
- Two or more patients on study drug experience a similar adverse event that is a CTCAE Grade 3 or higher other than ALT elevation.
- The Principal Investigator and the Sponsor consider that the number and/or severity of adverse events justify discontinuation of the study.
- The Sponsor unilaterally requests it.

Safety reviews for study stopping will be conducted jointly between medically qualified representatives of the Sponsor and Investigator and a joint decision will be made.

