9.1 Adverse events

An adverse event (AE) is any untoward medical occurrence (i.e., any unfavorable and unintended sign [including abnormal laboratory findings], symptom or disease) in a patient or clinical investigation patient *after providing written informed consent* for participation in the study until the end of study visit. Therefore, an AE may or may not be temporally or causally associated with the use of a medicinal (investigational) product.

In addition, all reports of intentional misuse and abuse of the study treatment are also considered an adverse event irrespective if a clinical event has occurred. See [Section 9.5](#) for an overview of the reporting requirements.

The occurrence of adverse events must be sought by non-directive questioning of the patient at each visit during the study. Adverse events also may be detected when they are volunteered by the patient during or between visits or through physical examination finding, laboratory test finding, or other assessments.

Abnormal laboratory values or test results constitute adverse events only if they fulfill at least one of the following criteria:

- they induce clinical signs or symptoms,
- they are considered clinically significant,
- they require therapy.

Clinically significant abnormal laboratory values or test results should be identified through a review of values outside of normal ranges/clinically notable ranges, significant changes from baseline or the previous visit, or values which are considered to be non-typical in patients with underlying disease. Investigators have the responsibility for managing the safety of individual patient and identifying adverse events. Alert ranges for liver and kidney related events are included in [Section 9.3](#) and [Section 9.4](#), respectively.

Adverse events must be recorded on the Adverse Events CRF under the signs, symptoms or diagnosis associated with them, and accompanied by the following information:

1. the Common Toxicity Criteria (CTC) AE grade (version 4.0 or higher) for the adverse event. If CTC-AE grading does not exist for an adverse event, use:
 - 1 = mild,
 - 2 = moderate,
 - 3 = severe
 - 4 = life threatening* (see [Section 9.2](#) for definition of a serious adverse event (SAE))
*Note: There may be cases where a CTCAE with a grade of 4 (life-threatening) may not necessarily be an SAE (e.g. certain laboratory abnormalities in the absence of meeting other seriousness criteria).

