All follow-up information, and the procedures performed must be recorded as appropriate in the CRF.

Table 9-2 Actions required for Liver Events

Criteria	Actions required	Follow-up monitoring
Potential Hy's Law case ^a	
 • Discontinue the study drug immediately • Hospitalize, if clinically appropriate • Establish causality 	ALT, AST, TBL, Alb, PT/INR, ALP and GGT until resolution ^c (frequency at investigator discretion)
ALT or AST		
$> 8 \times$ ULN and $> 2 \times$ baseline value	
 • Discontinue the study drug immediately • Hospitalize if clinically appropriate • Establish causality 	ALT, AST, TBL, Alb, PT/INR, ALP and GGT until resolution ^c (frequency at investigator discretion)
$> 3 \times$ ULN and $> 2 \times$ baseline value and INR > 1.5	
 • Discontinue the study drug immediately • Hospitalize, if clinically appropriate • Establish causality 	ALT, AST, TBL, Alb, PT/INR, ALP and GGT until resolution ^c (frequency at investigator discretion)
$> 5 \times$ ULN and $> 2 \times$ baseline value but $\leq 8 \times$ ULN	
 • Repeat LFT within 48 hours • If elevation is confirmed, refer to Table 6-3 	Refer to Table 6-3 ALT, AST, TBL, Alb, PT/INR, ALP and GGT until resolution ^c (frequency at investigator discretion)
$> 3 \times$ ULN and $> 2 \times$ baseline value, accompanied by symptoms ^b	
 • Discontinue the study drug immediately • Hospitalize if clinically appropriate • Establish causality 	Refer to Table 6-3 ALT, AST, TBL, Alb, PT/INR, ALP and GGT until resolution ^c (frequency at investigator discretion)

Criteria	Actions required	Follow-up monitoring
> 3 to ≤ 5 × ULN if normal baseline or >2 × baseline if elevated before drug exposure (patient is asymptomatic)	
 Repeat LFT within 48-72 hours If elevation is confirmed, refer to Table 6-3 	
Refer to Table 6-3
 
Investigator discretion

ALP (isolated)		
> 2 × ULN if normal baseline (in the absence of known bone pathology)	
 Repeat LFT within 48 hours If elevation persists, establish causality Complete liver CRF 	
Investigator discretion
 
Monitor LFT within 1 to 4 weeks or at next visit

TBL (isolated)		

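### As visible, bullet 2 of Protocol 7.5 exempts ALT elevation of any size from the two-patient Grade 3 hold, including the isolated rise that ends a patient's treatment at once

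*Protocol*

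**What the plan says.** Protocol 7.5 lists four conditions that pause new dosing pending review:

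- Bullet 1: one patient with a Grade 4 or higher event classified as related to study drug.
- Bullet 2: "Two or more patients on study drug experience a similar adverse event that is a CTCAE Grade 3 or higher other than ALT elevation".
- Bullet 3: the investigator and sponsor judge that the number or severity of events warrants stopping.
- Bullet 4: the sponsor asks for it.

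Only bullet 2 mentions ALT.

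At patient level, the top row of Table 6-3 (isolated ALT/AST elevations) is ">2 x baseline AND >8 x ULN". Its first action is to discontinue, with no repeat test and no dose reduction. Table 9-2 has the same threshold and says "Discontinue the study drug immediately". It gives the same instruction for potential Hy's Law cases and for > 3 × ULN and > 2 × baseline with INR > 1.5 or with symptoms.

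Section 4.2 excludes patients with "ALT or AST > 5 × ULN", and Section 4 allows ALT no tolerance around its limits. Section 10.4 says that a data monitoring committee is not required. Section 3.2 says "the Novartis Clinical Trial Team (CTT) will be unblinded throughout the study".

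**The concern.** There are good reasons to exempt some ALT rises. Patients enter with raised ALT, ALT is the primary efficacy variable, and Section 6.6 manages many rises by reducing the dose. None of these reasons reaches the > 8 × ULN row: the entry cap and the doubling condition rule out a raised baseline as the sole explanation, and no dose reduction is offered.

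The protocol thus treats the event as serious enough to end one patient's treatment at once, yet does not count it in the one rule that looks for a repeated Grade 3 event. Bullet 2 needs no causality judgement, and that is the protection lost for ALT. At stake is whether new patients go on being dosed after a second such case without a pre-set pause. Section 1.1 describes this as a first-in-patient study, and safety is a primary objective.

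**Working it through.** The plan states no operating characteristic for the hold rule, so there is no figure to reproduce. The check compares the texts and adds a small calculation for scale.

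**1. Can a permitted baseline alone produce the row?** For a baseline of b × ULN, the value must exceed max(8, 2b) × ULN. The largest b allowed at entry is 5 (Section 4.2).

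| Baseline (× ULN) | Must exceed (× ULN) | As a multiple of baseline |
|---|---|---|
| 1 | 8 | 8.0 |
| 2 | 8 | 4.0 |
| 3 | 8 | 2.7 |
| 4 | 8 | 2.0 |
| 5 | 10 | 2.0 |

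Every qualifying value is more than double baseline.

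**2. Which 7.5 condition catches an isolated ALT event in this row?**

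| Grade and causality | What applies |
|---|---|
| Grade 3 | Bullets 3 and 4 only (discretion) |
| Grade 4, related | Bullet 1, at one patient |
| Grade 4, not related | Bullets 3 and 4 only (discretion) |
| Below Grade 3 | Bullet 2 would not count any kind of event |

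Section 9.1 uses CTC grades (version 4.0 or higher), but the documents print no ALT cut-offs, and 7.5 adds that grading uses clinical judgement. That this row is often Grade 3 is an assumption.

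**3. The combined rows.** Section 9.1 says "Adverse events must be recorded on the Adverse Events CRF under the signs, symptoms or diagnosis associated with them". A case of raised ALT with bilirubin, INR or symptoms might therefore be entered as ALT elevation (exempt) or under another term (counted). These rows are ambiguous rather than exempt.

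**4. Any other study-level count?** None is visible. Section 9.7 only refers back to criteria given earlier.

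**5. Scale.** About 64 patients receive LMB763 in each cohort (Section 3.1). I read patients on study drug as LMB763 patients. For other similar Grade 3 events, two patients are 2/64 = 3.1% of one cohort, or 2/128 = 1.6% of both; Section 7.5 sets no cohort limit on the count. If ALT events in this row counted, with assumed rate p:

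P(X ≥ 2) = 1 − (1 − p)^n − n p (1 − p)^(n−1)

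| Assumed p | n = 64 | n = 128 |
|---|---|---|
| 1% | 0.135 | 0.367 |
| 2% | 0.367 | 0.728 |
| 5% | 0.836 | 0.989 |

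The last column also assumes the same rate at both doses. As written, isolated ALT events trigger bullet 2 with probability 0 at any rate.

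For a given n, these are upper figures for the added effect of a cap, for two reasons. They include related Grade 4 events, which bullet 1 already catches at one patient. They also include second events after the last patient has started, when there is no new dosing left to pause.

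**The case against.** The strongest reply is that the exemption is deliberate and that judgement replaces a count. Section 3.2 keeps the trial team unblinded precisely because safety measures such as ALT overlap with efficacy. Section 7.2 likewise separates liver and renal events from its general Grade 3 discontinuation rule. Every ALT above 3 × ULN is captured as a liver event, and bullet 3, which has no ALT exemption, describes a cluster of such events well. All of this stands as mitigation. It does not explain why the exemption has no ceiling, and it replaces a fixed trigger with discretion.

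Redaction also limits the point. Section 3.6 is blacked out, as are text in Section 3.7 and SAP Section 3. Criteria there may bear on this, so the conclusion covers the visible text only.

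Stronger readings are tempting, but the documents do not support them:

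- **ALT events escape every stopping rule.** They do not: bullets 1, 3 and 4 still apply.
- **Liver signals go unreviewed.** The sponsor team sees unblinded data throughout.
- **All liver enzyme events are exempt.** Only ALT is named, so two similar Grade 3 AST elevations would count.
- **The protocol clearly says what to do in every Table 9-2 row that stops the drug.** The symptomatic row is unsettled. Section 6.6 counts a symptomatic rise above 3 × ULN as a significant increase and reduces the dose once it is confirmed. The same section also says "If the patient has symptoms or other LFT abnormalities, in particular elevations of bilirubin and/or PT/INR and/or ALP), refer to" Section 9.3 and Table 9-2, where the row says to stop at once but points back to Table 6-3 for follow-up.

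**Conclusion.** The point holds in a limited form. In the visible text, two LMB763 patients with isolated ALT > 8 × ULN and > 2 × baseline do not force a hold unless one event is Grade 4 and related, or the investigator and sponsor decide on one. Two similar Grade 3 events of any other kind, AST elevation included, do force it.

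The size of the gap cannot be fixed from the documents. It depends on how often this row is Grade 3 (or Grade 4 and judged unrelated) and on an event rate that is not given. The figures of 13%, 37% and 84% for at least 2 of 64 are illustrations at assumed rates, not predictions of useful holds. The change is worth making as a modest safety improvement, because it is cheap and uses thresholds already in the protocol.

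**What to change.** Keep the exemption in bullet 2 of 7.5 but cap it, for example:

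> … other than ALT elevation; however, ALT > 8 × ULN and > 2 × baseline, ALT > 3 × ULN and > 2 × baseline with INR > 1.5, and potential Hy's Law cases do count and are treated as similar events.

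This brings in the isolated row, settles the INR and Hy's Law rows whatever term the site enters, and makes clear that the listed cases add up together. The amendment should also say whether the bullet's Grade 3 condition still applies to them; the calculation above leaves the grade to the assumed rate.

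Leave out the symptomatic > 3 × ULN row until Section 6.6 and Table 9-2 are reconciled. Rises first managed by dose reduction stay exempt, including those covered by the rule that if "a patient has persistent or new significant ALT and/or AST elevations, the patient must be discontinued from study treatment", unless they reach a listed criterion.

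The cost is one clause by amendment, with no extra tests or visits. The downside is a possible extra pause in new dosing for the joint review that 7.5 already describes. Patients on treatment without safety concerns could continue.
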